## Methods:

The MPOG Consortium assembles a database of perioperative information of patients undergoing anesthetic care at institutions across the US and the Netherlands. Data is assembled from electronic health record systems (including anesthesia specific systems), administrative, laboratory and outcome data sources. Full details of the functioning of the MPOG Consortium are described elsewhere. IRB approval for this study is provided by University of Michigan Institutional Review Board (HUM00052066). Sites participating in the MPOG collaborative obtain local IRB approval to assemble, organize and transmit this dataset. In keeping with the normal operating procedure of the MPOG collaborative the study protocol was presented to and approved by the MPOG Perioperative Clinical Research Committee (PCRC) on October 9th 2017. It was finalized on Feb 2nd 2018, prior to data extraction or analysis. A completed STROBE checklist for this study is attached to this manuscript (Appendix 1).

Sites will be included if they participated in the MPOG collaborative and data, including perioperative labs, and hospital and professional billing data were consistently available for the period between January 1, 2012 and July 1, 2017. We anticipate including data from 8 participating US sites: Cleveland Clinic, University of Colorado, University of Michigan, University of Oklahoma, University of Tennessee, University of Vermont, University of Virginia and Vanderbilt University.

Subjects will be included in the study if they were 18 years or older at time of surgery, underwent an orthopedic, general, transplant, vascular, gynecologic, urologic, neurosurgery, plastic, ENT or thoracic procedure with an associated inpatient stay. Subjects will be excluded if they underwent transfusion of greater than 3 units of packed red blood cells during the intraoperative period, underwent outpatient surgery, cardiac surgery, obstetric surgery, any procedure involving CPB or were assessed as having an ASA physical status classification of 5 or 6. Case groupings will be performed based on Anesthesia CPT Codes (see Appendix 2).

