The primary outcomes of this study are: the change in the pre-transfusion hemoglobin (ie transfusion threshold) and the nadir hemoglobin not-followed with an intraoperative transfusion over the course of the study period. The secondary outcomes of this study are: proportions of cases receiving a packed red blood cell transfusion throughout the study period (including stratification by prior laboratory measurements); the number of units of packed red blood cells transfused during the intraoperative period; the nadir postoperative hemoglobin (lowest value measured 0 – 72 hrs after the completion of intraoperative anesthesia care), the relationship between patient, surgical and institutional factors and the occurrence of transfusion and determination of the subsequent impact of any transfusion trends on blood product utilization; the relationship between in hospital mortality, post-operative myocardial injury, acute kidney injury and the pre-transfusion hemoglobin (for transfused cases – definition below) and lowest (for non-transfused cases) intraoperative hemoglobin.

In this study, we define coronary artery disease based on the present of a discharge ICD9/10 as listed in Appendix 3. Determination of AKI was based on the KIDIGO laboratory based definition AKI (Cr rise of 0.3 mg/dL rise within 48hrs of anesthesia end time or rise by more than 50% in 7 days). We will use intraoperative hemoglobin values documented, regardless of method of measurement. We preferentially use hemoglobin measures over hematocrit if these are documented simultaneously. If only a hematocrit is present at the time of lab measurement, we will perform an estimated conversion to hemoglobin, by dividing by 3. For blood transfusions documented exclusively in volume based units, we will convert this to units by assuming that any blood volume transfused greater than or equal to 250ml and less than or equal to 450 ml in one charting increment corresponds to one unit of blood.

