### **Statistical Analysis:**

Summary statistics will be presented as means and standard deviations or medians with interquartile ranges for continuous variables, as appropriate, and frequencies with percentages for categorical variables. All continuous variables will be assessed for normality using the Kolmogorov-Smirnov test. Univariate demographic and covariate comparisons between those who did and did not receive a transfusion will be analyzed using Student’s t-tests or Mann-

Whitney U tests for continuous variables, and Chi-squared or Fisher's Exact tests for categorical variables, as appropriate.

Mixed-effects multivariable linear or logistic regression models will be constructed as necessary. Prior to model entry, all covariates selected for model inclusion will be checked for collinearity using a Pearson correlation matrix. Variable pairs with a correlation  $> 0.70$  will be considered collinear and either combined into one variable, or one of the covariates will be excluded from the model. All variable pairs with a correlation  $\leq 0.70$  will be deemed fit for model entry. Model effect size will be presented as adjusted odds ratios with 95% confidence intervals, or beta coefficients with standard error, as appropriate. The covariates to be included in all models (discussed below) are surgical specialty, age, BMI, sex, presence of coronary artery disease, Elixhauser comorbidities, quarter of the study period, and hemoglobin. Time will be included in all models as a fixed effect by quarter, half-year, or year based on available sample size. The first quarter, half-year, or year will serve as the reference group. The random effects of institution and attending, where appropriate, will be presented as intraclass correlation coefficients and median odds ratios with 95% confidence intervals. Measures of effect size will be reported as adjusted odds ratios for logistic regression and beta coefficients for linear regression, and will be presented with 95% confidence intervals. For logistic regression models, model predictive capability will be presented as the area under the receiver operating curve (ROC) c-statistic. For linear regression, the extent to which the model explains the variability of the data will be presented as  $R^2$  values. Covariates with a statistically significant adjusted odds ratio or beta coefficient (as appropriate) will be considered independent predictors of the outcome.

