**Secondary Outcome 2: The number of units of packed red blood cells transfused during the intraoperative period.**

The number of units of pRBC transfused during the intraoperative period will be analyzed similar to Primary Outcome 1.

To determine independent predictors of the number of units of pRBC transfused during a case, two mixed effects linear regression models will be constructed with the independent covariates listed in the methods and the dependent variable of number of units of packed red blood cells transfused. The first model will contain the mixed effect of institution, and the second model will contain the hierarchical mixed effects of primary attending nested within institution.

**Secondary Outcome 3: The nadir postoperative hemoglobin (lowest value measured 0 – 72 hrs after the completion of intraoperative anesthesia care)**

The lowest postop hemoglobin will be examined for a trend over time for all cases using a Joinpoint analysis as for previous outcomes. The lowest postop hemoglobin will be compared at each time point between those with and without an intraoperative transfusion using a Student's t test or Mann-Whitney U test, as appropriate.

**Secondary Outcome 4: The relationship between patient, surgical and institutional factors and the occurrence of transfusion and determination of the subsequent impact of any transfusion trends on blood product utilization.**

Two mixed-effects logistic regression models will be used to determine if surgery type, year, and cardiac disease are independent predictors of intraoperative transfusion. The outcome of intraoperative transfusion will be defined as any PRBC use between Anesthesia Start and

Anesthesia End. The first model will contain the mixed effect of institution, and the second model will contain the hierarchical mixed effects of primary attending nested within institution. Independent variables to be included in the model are: Age, Sex, Elixhauser co-morbidities (as numeric and also CAD y/n, heart failure y/n, cancer y/n), WHO BMI classifications, ASA Status, Pre-op Hb, lowest Intra-op Hb for cases without intraop transfusion or the pre-transfusion hemoglobin, Pre-op Plts (abnormal y/n), Pre-op Creatinine (abnormal y/n), Abnormal coags (y/n – PT, PTT or INR), Surgical Specialty, EBL, Cell saver (Scavenged) blood use (y/n), Emergent Surgery, Use of anti-fibrinolytics (Aminocaproic Acid, Tranexamic Acid, Aprotinin) – y/n, and surgical Case Duration.

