## Sample Size:

Based on a rough approximation of the inclusion criteria using DataDirect, we found around 113,000 cases with intraoperative Hemoglobin/Hematocrit values, which should provide sufficient power for all planned analyses.

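### Pre-operative platelets and creatinine enter the Secondary Outcome 4 models only as abnormal y/n flags, which discards information and may leave avoidable residual confounding of unknown size

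*Protocol*

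**What the plan says.** Under Secondary Outcome 4 the protocol specifies two mixed-effects logistic models of intraoperative transfusion, meant to "determine if surgery type, year, and cardiac disease are independent predictors of intraoperative transfusion". The prescribed covariates include "Pre-op Plts (abnormal y/n), Pre-op Creatinine (abnormal y/n"). No cut-off is given, and nothing says whether abnormal means low, high or either. Pre-operative hemoglobin, blood loss and case duration stand in the same list without y/n coding.

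The section then describes a linear model of intraoperative hemoglobin that uses this covariate list plus a transfusion indicator. Its adjusted means serve as a proxy for the transfusion threshold.

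Four other statements bear on the point:
- Methods makes it a condition of site inclusion that data "including perioperative labs, and hospital and professional billing data were consistently available".
- Methods defines AKI by a "Cr rise of 0.3 mg/dL rise within 48hrs of anesthesia end time or rise by more than 50% in 7 days", which cannot be applied without numeric creatinine.
- Sample Size reports that "we found around 113,000 cases with intraoperative Hemoglobin/Hematocrit values".
- Statistical Analysis sets the reporting rule: "Covariates with a statistically significant adjusted odds ratio or beta coefficient (as appropriate) will be considered independent predictors of the outcome".

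**The concern.** Replacing a measured value by a flag treats every patient on the same side of the cut as alike. If transfusion risk varies with the value within those groups, and the value also differs between patients with and without cardiac disease, the flag adjusts only in part. What it misses is carried by the other coefficients.

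That matters here because the model exists to judge individual predictors, and cardiac disease is named in Aim 2. The reporting rule rests on statistical significance alone, so in a large sample a modest residual distortion could be enough for a factor to be labelled an independent predictor. The protocol gives no reason for the flags, and neither the data nor the sample size appears to require them.

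**Working it through.** The protocol states no figure on this point, so there is nothing to reproduce. It also gives no share abnormal, no lab distribution, and no association of either lab with transfusion or cardiac disease. Every input below is therefore an assumption, used only to show the range.

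**1. Analytic share remaining.** Assume a normal lab with a linear effect, weakly related to the exposure, cut on one side so that a share p is abnormal. The squared correlation between value and flag is φ(z)²/[p(1−p)], where z is the normal quantile with upper tail p. The share of that lab's confounding left after adjusting for the flag is 1 − φ(z)²/[p(1−p)].

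| p | z | φ(z)² | p(1−p) | captured | remaining |
|---|---|---|---|---|---|
| 5% | 1.645 | 0.0106 | 0.0475 | 22% | 78% |
| 10% | 1.282 | 0.0308 | 0.0900 | 34% | 66% |
| 20% | 0.842 | 0.0784 | 0.1600 | 49% | 51% |
| 30% | 0.524 | 0.1209 | 0.2100 | 58% | 42% |
| 50% | 0 | 0.1592 | 0.2500 | 64% | 36% |

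The remaining share passes 50% at p of about 21%.

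**2. Logistic simulation, true cardiac odds ratio 1.00.** Six runs of 150,000 cases were averaged, with cardiac disease in 20%, the lab 0.4 SD higher in cardiac patients, and a log odds ratio of 0.4 per SD. With a linear effect and a one-sided cut, the cardiac odds ratio was:
- no lab adjustment: 1.15 to 1.19
- y/n flag: 1.05 to 1.08
- continuous value: 0.99 to 1.02 (the spread around 1.00 is simulation error)

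The remaining share on the log scale, measured against continuous adjustment, is (ln OR flag − ln OR continuous)/(ln OR crude − ln OR continuous). At p = 10% this is (ln 1.083 − ln 0.997)/(ln 1.161 − ln 0.997) = 0.083/0.152 = 54%. The same calculation gives about 40% at p = 20%, 38% at 30% and 40% at 50%.

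**3. Other shapes of effect, same set-up.**
- Risk changes only at the cut: about 0% remains.
- Risk rises only beyond the cut: about 26% to 44% remains.
- A flag combining low and high values (20% flagged in all) with a linear effect: about 98% remains.

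**4. Second simulation, true cardiac odds ratio 1.10.** With 113,000 cases, a log odds ratio of 0.3 per SD and cardiac patients 0.3, 0.5 or 0.7 SD higher, the flag gave 1.12–1.14, 1.17–1.18 and 1.19–1.23. The continuous value gave 1.08–1.11. Total confounding is roughly 0.3 × shift = 0.09, 0.15 and 0.21. The excess over ln 1.10 with the flag is 0.018–0.036, 0.062–0.070 and 0.079–0.112, which is 20–40%, 41–47% and 37–53% of the total.

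**5. Against sampling error.** Assume 113,000 cases, 20% with cardiac disease and 5% or 10% transfused in both groups. The unadjusted standard error of the cardiac log odds ratio is √(1/1130 + 1/21470 + 1/4520 + 1/85880) = 0.034 at 5%, and 0.025 at 10%. A distortion of 1.05 to 1.08 (0.049 to 0.077 on the log scale) is then about 1.4 to 3.1 standard errors. Covariates and clustering would widen the standard error and lower these ratios.

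**The case against.** The strongest reply is that this is a modelling preference about two adjustment covariates in secondary models of a study described as descriptive. The protocol does not contradict itself here, and the same models already adjust for "Elixhauser co-morbidities (as numeric and also CAD y/n, heart failure y/n, cancer y/n), WHO BMI classifications, ASA Status, Pre-op Hb", together with coagulation results and blood loss. What counts is each lab's confounding after those terms, and nobody has estimated it. This stands: the calculations contain one lab and one exposure, so they describe a share of that lab's own confounding and not the distortion in the full model. It limits the size that can be claimed, but gives no reason for discarding the values.

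Three stronger readings are tempting and are not supported:
- A reader might infer that at least half of the confounding is left in place. That needs a low share abnormal (about 21% or less on the analytic formula, nearer 10% in the first simulation) or a two-sided flag, plus a linear effect throughout. The protocol supplies none of these, and most of the simulated one-sided shares fall below half.
- A reader might infer that abnormal merges low with high results. The wording allows it but does not say so; it could equally mean low platelets and high creatinine. The exact definition may also be left to an analysis plan that is not at hand.
- A reader might take numeric values as established for both labs. For creatinine the AKI definition implies them; for platelets they are only inferred from the perioperative labs.

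**Conclusion.** The point holds as a minor one. The protocol prescribes the y/n coding, so this is a stated choice and not a detail left open, and a better method is available at little cost. The coding discards information and may leave avoidable residual confounding in the adjusted odds ratios of Secondary Outcome 4, including the one for cardiac disease, and in the linear model that reuses the list.

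The size is unknown. About one third to three quarters of each lab's own linear confounding is an illustration that rests on a one-sided cut, a normal lab, a linear effect and 5% to 50% abnormal. Other shapes of effect and other definitions of the flag take the range from near zero to nearly all. The documents do not show that the cardiac-disease odds ratio would be materially wrong, or that its label as an independent predictor would change. Neither primary outcome uses these covariates.

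**What to change.** In the Secondary Outcome 4 covariate list, replace the two flags by pre-operative platelet count and log creatinine as continuous terms with restricted cubic splines. State that the linear model reusing the list takes the same terms, and how cases with no pre-operative value are handled. Splines allow for a threshold or a two-sided relation without having to define abnormal.

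The cost is a few degrees of freedom, a plot in place of a single odds ratio for each lab, and the explicit rule for missing values. No new data collection is expected, provided numeric platelet counts are confirmed in the extract. Because Methods says the protocol was finalized before data extraction, the change should be recorded as a dated amendment.

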## Sample Size:

Based on a rough approximation of the inclusion criteria using DataDirect, we found around 113,000 cases with intraoperative Hemoglobin/Hematocrit values, which should provide sufficient power for all planned analyses.

## Appendix 1 – Completed STROBE Statement

STROBE Statement—checklist of items that should be included in reports of observational studies

|                              | Item No | Recommendation   | Result |
|------------------------------|---------|--|--------|
| Title and abstract    | 1       | (a) Indicate the study's design with a commonly used term in the title or the abstract   | Y      |
|                              |         | (b) Provide in the abstract an informative and balanced summary of what was done and what was found  | N/A    |
| Introduction          |         |  |        |
| Background/rationale         | 2       | Explain the scientific background and rationale for the investigation being reported   | Y      |
| Objectives                   | 3       | State specific objectives, including any prespecified hypotheses   | Y      |
| Methods               |         |  |        |
| Study design                 | 4       | Present key elements of study design early in the paper  | Y      |
| Setting                      | 5       | Describe the setting, locations, and relevant dates, including periods of recruitment, exposure, follow-up, and data collection  | Y      |
| Participants                 | 6       | (a) Cohort study —Give the eligibility criteria, and the sources and methods of selection of participants. Describe methods of follow-up  | Y      |
|                              |         | Case-control study —Give the eligibility criteria, and the sources and methods of case ascertainment and control selection. Give the rationale for the choice of cases and controls |        |
|                              |         | Cross-sectional study —Give the eligibility criteria, and the sources and methods of selection of participants  |        |
|                              |         | (b) Cohort study —For matched studies, give matching criteria and number of exposed and unexposed   | N/A    |
|                              |         | Case-control study —For matched studies, give matching criteria and the number of controls per case   |        |
| Variables                    | 7       | Clearly define all outcomes, exposures, predictors, potential confounders, and effect modifiers. Give diagnostic criteria, if applicable   | Y      |
| Data sources/
measurement | 8*      | For each variable of interest, give sources of data and details of methods of assessment (measurement). Describe   | Y      |

comparability of assessment methods if there is more than one group

|                        |    |   |     |
|------------------------|----|---|-----|
| Bias                   | 9  | Describe any efforts to address potential sources of bias   | N/A |
| Study size             | 10 | Explain how the study size was arrived at   | Y   |
| Quantitative variables | 11 | Explain how quantitative variables were handled in the analyses. If applicable, describe which groupings were chosen and why  | Y   |
| Statistical methods    | 12 | (a) Describe all statistical methods, including those used to control for confounding   | Y   |
|                        |    | (b) Describe any methods used to examine subgroups and interactions   | Y   |
|                        |    | (c) Explain how missing data were addressed   | N/A |
|                        |    | (d) Cohort study —If applicable, explain how loss to follow-up was addressed

Case-control study —If applicable, explain how matching of cases and controls was addressed

Cross-sectional study —If applicable, describe analytical methods taking account of sampling strategy | Y   |
|                        |    | (e) Describe any sensitivity analyses   | N/A |

## Results

|                  |     |   |     |
|------------------|-----|---|-----|
| Participants     | 13* | (a) Report numbers of individuals at each stage of study—eg numbers potentially eligible, examined for eligibility, confirmed eligible, included in the study, completing follow-up, and analysed | N/A |
|                  |     | (b) Give reasons for non-participation at each stage  | N/A |
|                  |     | (c) Consider use of a flow diagram  | N/A |
| Descriptive data | 14* | (a) Give characteristics of study participants (eg demographic, clinical, social) and information on exposures and potential confounders  | N/A |
|                  |     | (b) Indicate number of participants with missing data for each variable of interest   | N/A |
|                  |     | (c) Cohort study —Summarise follow-up time (eg, average and total amount)  | N/A |
| Outcome data     | 15* | Cohort study —Report numbers of outcome events or summary measures over time   | N/A |
|                  |     | Case-control study —Report numbers in each exposure category, or summary measures of exposure  | N/A |

|                          |    |  |     |
|--------------------------|----|--|-----|
|                          |    | Cross-sectional study —Report numbers of outcome events or summary measures   | N/A |
| Main results             | 16 | (a) Give unadjusted estimates and, if applicable, confounder-adjusted estimates and their precision (eg, 95% confidence interval). Make clear which confounders were adjusted for and why they were included | N/A |
|                          |    | (b) Report category boundaries when continuous variables were categorized  | N/A |
|                          |    | (c) If relevant, consider translating estimates of relative risk into absolute risk for a meaningful time period   | N/A |
| Other analyses           | 17 | Report other analyses done—eg analyses of subgroups and interactions, and sensitivity analyses   | N/A |
| Discussion        |    |  |     |
| Key results              | 18 | Summarise key results with reference to study objectives   | N/A |
| Limitations              | 19 | Discuss limitations of the study, taking into account sources of potential bias or imprecision. Discuss both direction and magnitude of any potential bias   | N/A |
| Interpretation           | 20 | Give a cautious overall interpretation of results considering objectives, limitations, multiplicity of analyses, results from similar studies, and other relevant evidence                                   | N/A |
| Generalisability         | 21 | Discuss the generalisability (external validity) of the study results  | N/A |
| Other information |    |  |     |
| Funding                  | 22 | Give the source of funding and the role of the funders for the present study and, if applicable, for the original study on which the present article is based  | Y   |

\*Give information separately for cases and controls in case-control studies and, if applicable, for exposed and unexposed groups in cohort and cross-sectional studies.

**Note:** An Explanation and Elaboration article discusses each checklist item and gives methodological background and published examples of transparent reporting. The STROBE checklist is best used in conjunction with this article (freely available on the Web sites of PLoS Medicine at <http://www.plosmedicine.org/>, Annals of Internal Medicine at <http://www.annals.org/>, and Epidemiology at <http://www.epidem.com/>). Information on the STROBE Initiative is available at [www.strobe-statement.org](http://www.strobe-statement.org).

